9.1 Calculating the size of the study

The calculation of the number of subjects required is based on the number of explanatory variables to be included in the multiple logistic regression model to construct the ultrasound score. The "1 variable per 10 events" rule is applied. (61)

A total of 5 variables will be collected and analysed as described above (see 9.5), with an estimated prevalence of swallowing disorders of 50%.

There are therefore potentially 5 variables to be included in the predictive model, i.e. a required number of 100 patients.

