3.2 Secondary outcomes

The secondary outcomes will be :

- To evaluate the diagnostic accuracy and reproducibility of the ultrasound score in the diagnosis of swallowing disorders
- To evaluate the reproducibility and diagnostic accuracy of hyoid bone ascension in the diagnosis of swallowing disorders
- To evaluate the reproducibility and diagnostic accuracy of the digastric muscle thickening fraction in the diagnosis of swallowing disorders
- To evaluate the reproducibility and diagnostic accuracy of the genohyoid thickening fraction in the diagnosis of swallowing disorders
- To evaluate the reproducibility and diagnostic accuracy of the amount and duration of lingual movement in the diagnosis of swallowing disorders

4 Eligibility criteria

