7.2 Practical details of the ultrasound examination

The examination, the details of which can be found in **Appendix 4**, is carried out using a Sonoscape Expert 2 ultrasound scanner (Digital Color Doppler Ultrasound System; Sonoscape medical corp. China) equipped with a linear probe (7-10 MHZ) and a convex probe (3-5 MHZ). Both probes will be used for each of the swallowing trials.

In order to assess inter- and intra-examiner reliability, the tests will be performed by two different operators and twice by the same operator, i.e. 3 identical examinations in total, in the first 20 patients included.

The duration of an examination will not exceed 15 minutes, i.e. a total duration of the ultrasound examination of 45 minutes for the first 20 patients (15 minutes for examination, 3 examinations).

The patient is in a sitting position and performs salivary swallowing attempts on request of the operator.

The convex probe will be placed under the chin, in the sagittal plane and between the edges of the hyoid bone and the mandible. The acoustic shadows of these bones will allow us to localise the structures and centre the image. (53)(54)

The following elements will be assessed:

- The position of the hyoid bone at rest and during swallowing;
- The thickness of the geniohyoid at rest and during swallowing;
- The contractility of the tongue ;
- The duration of contraction of the geniohyoid ;
- The number of swallowing attempts.

The linear probe will also be placed submentally, along a transverse axis, in order to qualitatively and quantitatively evaluate the suprahyoid muscles (55)

Qualitative analysis will be performed using the Heckmatt Score. (56) Quantitative analysis will be performed by measuring the thickness of the muscles at rest and during contraction. These two measurements will be used to calculate its thickening fraction. The thickness of the muscle is calculated by quantifying the distance between the upper and lower fascia of the muscle.

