7.3 Semiology in aerodigestive tract ultrasound

The different dysfunctions of the structures or functions involved in swallowing can be defined on ultrasound by the following signs

- (1) Lingual dysfunction (53)(57)(54):
 - a. Abnormal movement pattern ;
 - b. Several attempts identified;
 - c. Decreased range of motion ;
 - d. Decrease in thickness.
- (2) Suprahyoid muscle dysfunction (58)(59) :
 - a. Decrease in signal strength ;
 - b. Fat invasion and poorly defined muscle boundaries;
 - c. Decrease in thickness or surface area compared to contralateral ;
 - d. Decreased mobility and thickening fraction compared to contralateral.
- (3) Genohyoid dysfunction (55)(60) :
 - a. Decreased thickening fraction.
- (4) Laryngeal ascension defect (60)(58) :
 - a. Ascension <1.5cm. measured indirectly by assessment of hyoid bone ascension.

8 Conduct of the research

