9.3 Potential variables of the ultrasound score

Structures assessed		Results	Weighting
Language			
	Abnormal movement	Yes/No	
	> 1 attempt identified	Yes/No	
	Range of motion	< threshold > threshold (only to be defined)	
	Thickness	< threshold > threshold (threshold to be defined)	
Suprahyoid muscles			
	Signal strength (Heckmatt score)	1-4	
	Poorly defined fat involution and muscle boundaries	Yes/No	
	Decreased surface area compared to contralateral	Surface < threshold (threshold to be defined)	
	Thickening fraction compared to contralateral	< threshold > threshold (only to be defined)	
Geniohyoid			
	Decreased thickening fraction	< threshold > threshold (only to be defined)	
Laryngeal ascension			
	Ascension measured indirectly by assessment of hyoid bone ascension	< threshold > threshold (only to be defined)	

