9.4 Determination of classes and thresholds of quantitative variables

The hypothesis of a linear relationship between the logit of the diagnosis of swallowing disorders objectified by VFSS and the quantitative variable will be tested. If it is verified, the variable will be dichotomised. The threshold used will be determined using ROC (Receiver

Operating Characteristic) curve analysis, which will allow the threshold for which sensitivity and specificity are maximum to be retained. (62)

The variables for which the hypothesis is not verified will be split into classes. (63)

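### Section 9.1 justifies 100 patients with five variables, but 9.5 names none and the score's only candidate list (9.3) has ten: about 5 events per candidate, not 10

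*Combined protocol and SAP*

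**What the plan says.** Section 9.1 rests the sample size on the "number of explanatory variables to be included in the multiple logistic regression model to construct the ultrasound score" and applies a rule of 10 events per variable. It continues: "A total of 5 variables will be collected and analysed as described above (see 9.5), with an estimated prevalence of swallowing disorders of 50"%. It concludes: "There are therefore potentially 5 variables to be included in the predictive model, i.e. a required number of 100 patients".

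Section 9.5, to which 9.1 points, defines the VFSS-positive and VFSS-negative groups and a univariate screen at p < 0.20. It names no variable and sets no maximum. Section 9.6 enters every variable that passes the screen, selects by AIC and checks for multicollinearity. It sets no maximum either.

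The list headed as potential score variables is in 9.3. It has ten rows: four for the tongue, four for the suprahyoid muscles, one for the geniohyoid and one for hyoid ascension. Section 7.3 also sets out ten signs under these four structures, with small differences of wording; for example, "Fat invasion and poorly defined muscle boundaries" in 7.3 becomes "Poorly defined fat involution and muscle boundaries" in 9.3. Six of the ten rows in 9.3 need a threshold. Where 9.4 dichotomises a variable, it uses ROC analysis, "which will allow the threshold for which sensitivity and specificity are maximum to be retained".

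The primary outcome (3.1) is the choice of variables for the score. Accuracy (9.7.2) is estimated in the same patients, and no internal validation is described.

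**The concern.** The five in 9.1 is the only input, apart from prevalence, that produces 100, and its cross-reference leads to a section without a list. If the candidates are the ten rows of 9.3, the stated ratio is halved. An analyst could also start from five or from ten variables and claim to follow the protocol either way, for an analysis whose primary result is which variables are chosen. A longer candidate list gives more chances for an uninformative variable to enter the score, and it increases the optimism of accuracy figures computed on the development data.

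**Working it through.** **The plan's figure.** N = variables x 10 / prevalence = 5 x 10 / 0.50 = 100. This reproduces 9.1.

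**With the list in 9.3.**
- Rows: 4 + 4 + 1 + 1 = 10.
- Expected events: 100 x 0.50 = 50.
- Events per candidate: 50 / 10 = 5.0, against 50 / 5 = 10.0 as stated.
- Same rule with ten: 10 x 10 / 0.50 = 200 patients. At the 4 per month of section 4.3 this is 200 / 4 = 50 months, against 25 planned.

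The 5.0 is an upper value. The Heckmatt score has four levels; as three indicators it brings the count to 12 parameters, and 50 / 12 = 4.2. Section 9.4 allows further splitting into classes, and Appendix 3 excludes patients whose videofluoroscopy is not completed. At an assumed prevalence of 40% or 60% the smaller group has 40 patients, giving 4.0 per candidate; at 30% or 70% it gives 3.0.

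**Can the five be found elsewhere?** Two lists can be read as five.
- Single measures in 3.2: hyoid ascension, digastric and geniohyoid thickening fractions, amount and duration of lingual movement ("To evaluate the reproducibility and diagnostic accuracy of the amount and duration of lingual movement in the diagnosis of swallowing disorders").
- Convex-probe items in 7.2, which include "The duration of contraction of the geniohyoid".

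Neither is labelled as the candidate set and 9.1 cites neither. Each contains a duration measure, and 9.3 has no duration row.

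**How many enter the model?** Assume 50 v 50 patients, independent normal candidates and informative ones shifted by 0.5 SD. The chance of passing p < 0.20 is then 0.887 for an informative candidate and 0.20 for a noise candidate. With ten candidates the mean number entering is:
- 3 informative: 3 x 0.887 + 7 x 0.20 = 4.1
- 5 informative: 5 x 0.887 + 5 x 0.20 = 5.4
- 10 informative: 10 x 0.887 = 8.9

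More than five enter in 11%, 47% and 99.7% of cases.

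**Consequence.** Simulation on the same assumptions: t-test screen, backward AIC, 2500 runs, three informative candidates.

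| | Ten candidates | Five candidates |
|---|---|---|
| No thresholds: false variables kept | 0.89 | 0.27 |
| At least one false variable | 61% | 25% |
| Apparent / true AUC | 0.760 / 0.685 | 0.746 / 0.697 |
| AUC optimism | 0.074 | 0.049 |
| All cut at ROC threshold: false variables kept | 1.22 | 0.34 |
| At least one false variable | 74% | 31% |
| Apparent / true AUC | 0.800 / 0.642 | 0.771 / 0.653 |
| AUC optimism | 0.159 | 0.119 |

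Optimism was computed before rounding. The longer list adds 0.074 - 0.049 = 0.025 without thresholds and 0.159 - 0.119 = 0.040 with them. A separate set of 1000 runs per cell gave 0.072 - 0.045 = 0.027 and 0.155 - 0.120 = 0.035. With six threshold rows the plan lies between the two cases. The chance of keeping any one noise candidate does not change (0.89 / 7 and 0.27 / 2, both about 0.13); there are seven of them instead of two.

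**The case against.** The strongest reply is that the rule in 9.1 counts variables in the model, not candidates, and that the word potentially signals an expected model size. With three informative candidates this looks reasonable: on average 4.1 enter, and final models exceed five variables in only 2% of runs (6% with thresholds). But 9.1 speaks of five variables collected and analysed, and infers from that the five to be included; the same inference from ten gives 200. No rule in 9.4 to 9.6 produces five, and the number surviving is known only after the outcome data have been used. With five or ten informative candidates, final models exceed five variables in 16% or 88% of runs (29% or 96% with thresholds). The multicollinearity check may remove a variable but is not a cap.

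It can also be said that the text of 7.2 and Appendix 4 does not name tongue thickness or muscle surface area as measurements, so perhaps only eight rows are collected. The figures of Appendix 4 are not available to settle this. Eight would give 50 / 8 = 6.25 events each, still short of 10.

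Three points stand. Most of the optimism is present with five candidates (0.049 of 0.074; 0.119 of 0.159), so it comes mainly from selection and same-sample evaluation. The extra amount is modest; a smaller set of 250 runs with thresholds put it at 0.149 - 0.130 = 0.019. And the five-candidate comparison assumes that the five include all three informative variables. In 600 runs per cell without thresholds, true AUC was 0.687 with ten candidates, 0.699 with five holding all three, and 0.661 with five holding two. A poorly chosen short list can cost more than a long one.

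**Conclusion.** The concern holds. The count in 9.1 and its reference to 9.5 do not agree with 9.3, and the stated 10 events per variable is about 5 per listed candidate at 50% prevalence, taking each row as one parameter. This conclusion needs only the documents and simple arithmetic. The consequence rests on the simulation assumptions above: roughly three to four times as many false variables in the score, and about 0.03 to 0.04 more AUC optimism (0.02 to 0.04 if the smaller run is included). It does not show that 100 patients is unusable. It shows that the justification given does not fit the analysis described.

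**What to change.** Keep N = 100 and reconcile 9.1, 9.3 and 9.5 by one of two routes.

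- **(a) Five candidates.** Name five one-parameter candidates in 9.3 and 9.5, chosen on prior grounds without reference to the VFSS outcome, and make the other rows descriptive. Ten events per variable then holds at 50% prevalence. The risk is losing informative variables: five drawn at random from ten would hold on average 5 x 3 / 10 = 1.5 of three.
- **(b) Ten candidates.** If five cannot be justified in advance, keep the ten, restate 9.1 as about 5 events per candidate and correct the reference to 9.5. The cost is a less favourable stated ratio.

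Under either route keep the p < 0.20 screen and AIC selection. Dropping the screen raised false variables from 0.34 to 1.23 with five candidates and thresholds.

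In 9.7.2, report accuracy with a bootstrap optimism correction that repeats the 9.4 thresholds, the screen, the AIC selection and the score cut-off, beside the uncorrected values. This is worth doing with five candidates too. In 250 runs with 80 resamples each, the AUC bias left was 0.003 (ten) and -0.002 (five) without thresholds. With thresholds it fell from 0.149 to 0.038 (ten) and from 0.130 to 0.047 (five). The plan should therefore say that corrected values may still be somewhat high if thresholds are chosen on the data.

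Cost: no extra patients; wording in 9.1, 9.3 and 9.5 (route a) or 9.1 only (route b), plus 9.7.2 and a little more analysis time.

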1.1. Background to the onset of swallowing disorders

Swallowing disorders, although under-diagnosed (8) The prevalence of swallowing disorders, although under-diagnosed, can be as high as 30% in hospitalised patients. (11) This prevalence is particularly high in certain clinical situations such as neurological disorders or diseases like Parkinson's disease (80%) (12) neuromuscular diseases (80%) (13) or post-stroke (81%) (14). In head and neck cancers, especially after surgery, the prevalence can be as high as 61%; (15). In intensive care, they may be the consequence of intubation, tracheotomies and prolonged mechanical ventilation, (16)(17)(7) or even the reason for admission to the intensive care unit. (18)(5)

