1.2 Day hospital for swallowing disorders

Dysphagia is a historically important disorder at Forcilles because of its prevalence in the population admitted to hospital. Various health professionals are organised around the multidisciplinary management of these disorders in the different departments of the hospital. The need to bring together this expertise, in order to meet the growing demand from independent professionals and other surrounding health establishments, in particular the geriatric, acute medicine and ENT cancer departments, led to the creation of a swallowing day hospital (HDJ).

Most patients admitted to HDJ have sarcopenia, ENT cancers and/or have had long periods of mechanical ventilation and may still have a tracheostomy.

The HDJ therefore welcomes patients with the risk factors described above for swallowing disorders. The examinations that will be carried out are prescribed by the doctor responsible for the medical care of the patient.

The following equipment is available in the HDJ: an endoscopy column and the medical equipment necessary to monitor the patient's vital parameters; a radiology room with the necessary equipment for videofluoroscopy and two consultation rooms. Thus, within this HDJ, a doctor is involved, responsible for the unit, who ensures the medical evaluation of the patient, the carrying out of medical examinations when they are indicated and the submission of the end of hospitalisation report; a radiologist doctor who ensures the carrying out of imaging examinations; physiotherapists and speech therapists in charge of the clinical assessment of the patient and dieticians who carry out a consultation in order to detect and manage any undernutrition, and also to adapt the patient's diet to the food textures recommended by the speech therapists following their assessment.

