4.1 Inclusion criteria

Patients with the following criteria will be included:

- Patients admitted to the day hospital ;
- Patients with a medical indication for videofluoroscopy ;
- Medical prescription for physiotherapy assessment ;
- Ultrasound operator available;
- Patient at least 18 years old at the time of inclusion;
- Affiliation with a social security scheme or beneficiary of such a scheme ;
- Oral, free, informed and express consent of the patient.

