9.5 Selection of variables to be included in the score

Patients will be classified into 2 groups according to the diagnosis obtained with VFSS: positive group (presence of swallowing disorders) and negative group (absence of swallowing disorders). The ultrasound variables will be compared between the 2 groups by appropriate tests according to the type of variables (quantitative or qualitative) and their distribution. The results of these comparisons will be used to select the ultrasound variables showing a difference between the 2 groups ($p < 0.20$) for inclusion in the multivariate logistic regression. (62)(63)

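### The size of 100 rests on an unsourced 50% prevalence, the most favourable value possible; the smaller videofluoroscopy group may well not reach the 50 that five variables need

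*Combined protocol and SAP*

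**What the plan says.** **Sizing (section 9.1).** The plan states "The '1 variable per 10 events' rule is applied" and "A total of 5 variables will be collected and analysed as described above (see 9.5"). It combines these "with an estimated prevalence of swallowing disorders of 50" per cent to reach the total, "i.e. a required number of 100 patients". It gives no reference or local figure for the prevalence.

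**Outcome of the model (section 9.5).** "Patients will be classified into 2 groups according to the diagnosis obtained with VFSS", one positive and one negative.

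**Who is enrolled.** Section 4.1 requires "Patients with a medical indication for videofluoroscopy". Section 1.2 says "Most patients admitted to HDJ have sarcopenia, ENT cancers and/or have had long periods of mechanical ventilation". Section 10 describes suspected disorders mostly linked to ENT surgery or a long intensive care stay. Section 4.2 excludes total laryngectomy.

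**Prevalence figures in the background (section 1.1, onset of swallowing disorders).** Up to 30% in hospitalised patients; 80% in Parkinson's disease; 80% in neuromuscular disease; 81% after stroke. For one further group: "In head and neck cancers, especially after surgery, the prevalence can be as high as 61" per cent.

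**The concern.** The prevalence drives the sample size directly, yet it is the one input without support. A rule of ten per variable protects a binary logistic model only if it is applied to the less frequent outcome group. At 50% the two groups are equal and the smaller one is at its maximum, so any departure in either direction leaves fewer than 50 expected in the smaller group. The plan therefore has no margin.

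A departure upwards is plausible, because entry requires an indication for videofluoroscopy in a unit that receives patients at risk. If it occurs, fitting five variables to 100 patients would overload the model by the standard that section 9.1 itself adopts. The likely results are unstable variable selection and weights, and accuracy figures that look better in these patients than they would in new ones.

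**Working it through.** **Inputs.** Five variables, ten events per variable, prevalence p = 0.50 and N = 100 (section 9.1). Outcome classes: positive and negative on videofluoroscopy (section 9.5). Other values of p: the background figures in section 1.1, plus 40%, 55%, 60% and 70% as illustrative assumptions.

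**1. The plan's own figure.** N = (5 × 10) / 0.50 = 100. Reproduced exactly.

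**2. Which group counts.** The expected smaller group is 100 × min(p, 1 − p), which is largest at p = 0.50. Patients per variable is that number divided by 5. Variables supported is that number divided by 10, rounded down. The N that would put 50 in the smaller group is 50 / min(p, 1 − p), rounded up.

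| Prevalence | Expected smaller group | Per variable, five variables | Variables supported by 100 patients | N for 50 in smaller group |
|---|---|---|---|---|
| 30% | 30 | 6.0 | 3 | 167 |
| 40% or 60% | 40 | 8.0 | 4 | 125 |
| 50% | 50 | 10.0 | 5 | 100 |
| 55% | 45 | 9.0 | 4 | 112 |
| 61% | 39 | 7.8 | 3 | 129 |
| 70% | 30 | 6.0 | 3 | 167 |
| 80% | 20 | 4.0 | 2 | 250 |
| 81% | 19 | 3.8 | 1 | 264 |

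**3. The literal wording.** Section 9.1 speaks of events and does not mention the smaller group. If only affected patients count, 61% to 81% prevalence gives 61 to 81 events and the required 50 is met. But this reading works backwards. At 80% it would allow 80 / 10 = 8 variables with only 20 unaffected patients, or 20 / 8 = 2.5 unaffected patients per variable.

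**4. Sampling variation.** With X ~ Binomial(100, p) affected patients, the probability that the unaffected group reaches 50 is 0.54 at p = 50%, 0.18 at 55% and 0.016 at 61%. Even at a true 50%, both groups reach 50 only on an exact even split (probability 0.080), and the smaller group averages 46, or 46 / 5 = 9.2 per variable. That shortfall is small. It does mean that a limit based on the observed count would usually be four: the probability that the smaller group lies between 40 and 49 is 0.965 − 0.080 = 0.885.

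**The case against.** Nothing in the documents refutes 50%. It lies between the ceiling of 30% for inpatients and the ceiling of 61% for head and neck cancer. A reader might infer that the protocol's own figures of 61% to 81% apply to the enrolled patients, so that the smaller group is bound to miss 50. The documents do not support this:

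- The 80% and 81% figures are for Parkinson's disease, neuromuscular disease and stroke. Sections 1.2 and 10 do not name these as the main case mix.
- The 61% is worded as an upper figure. The title of its reference concerns laryngectomy and pharyngolaryngectomy, while section 4.2 excludes total laryngectomy.
- No prevalence is given for sarcopenia or for ventilated patients, two of the three groups that section 1.2 names.

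This part of the objection stands, and the shortfall is therefore conditional on the true prevalence.

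The events wording is also a fair reply on the text: read literally, a higher prevalence satisfies section 9.1. It does not answer the statistical point (step 3).

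A reader might further infer that poor precision on specificity would settle whether ultrasound can replace videofluoroscopy. No section says so. Section 9.7.2 lists sensitivity, specificity, predictive values and the diagnostic odds ratio without ranking them and sets no precision target. A higher prevalence would also sharpen sensitivity.

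Finally, ten per variable is a convention, and the title of the reference cited for it (61) disputes it. That weakens the rule itself, but the plan rests its size on nothing else.

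**Conclusion.** The concern holds in a limited form. The 50% is unsourced, the 100 depends on it, and it is the most favourable value the calculation could use. The smaller videofluoroscopy group may well not reach 50; whether it does depends on a prevalence that the documents do not establish. Over the background figures from 30% to 81%, the expected smaller group runs from its maximum of 50 down to 19, or from 10 to 3.8 per variable for five variables.

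The conclusion assumes that all 100 patients are analysed, that the rule is applied to the less frequent group (sound practice, but not what section 9.1 says), and that ten per variable is kept as the sponsor's standard. A prevalence above 50% is a plausible inference from the entry criteria, not a documented fact; one below 50% shrinks the smaller group just as much.

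**What to change.** Keep 100 patients and change section 9.1 as follows.

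1. **Apply the rule to the smaller group.** Suggested text: *The number of candidate variables (model degrees of freedom, counted before the p<0.20 screening in 9.5) will not exceed one tenth of the smaller VFSS group.* A limit set only after screening would not protect the model, because the screening already uses the outcome. The table in section 9.3 lists ten candidates, so some would have to be set aside even at 50%.
2. **Fix the timing and the order.** Count the two groups after the last inclusion and before any ultrasound variable is compared with videofluoroscopy. Drop candidates in a priority order written down in advance, so that the limit cannot be tuned to the results.
3. **Restate the size.** Suggested text: *100 patients support five variables only if prevalence is 50%; three at 61–70% or 30%, two at 80%.* These are expected counts, so the limit finally applied may differ by a variable or so.
4. **Justify the planning prevalence** from the unit's own past videofluoroscopy results, if available. Section 12 already draws on two years of admissions data. Section 9.5 does not say which finding makes a patient positive, so that definition must be fixed first and applied to the past results.

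The cost is a few sentences in section 9.1, a less favourable stated figure and possibly a shorter score. No extra patients are needed.
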